# **Protocol Amendment Summary of Changes Table**

DOCUMENT HISTORY	
Document	Date
Original Protocol	28-Oct-2022

# Amendment [a]

This amendment is considered to be nonsubstantial.

#### **Overall Rationale for the Amendment:**

The main rationale for the amendment is to clarify the chosen dosing regimens for treatment arms 3 and 4 and other minor corrections/clarifications as stated below.

Section # and Name	Description of Change	Brief Rationale
1.1. Synopsis	Updated visit frequency to every 2 weeks for the first 10 visits (V2-V10) and every 4 weeks thereafter	Correction per SoA
	Addition of "<5 half-lives prior to randomization" to an exclusion criterion about passive anti-amyloid immunotherapy	Clarification
1.2. Schema	Revised schema to align with every 2 weeks visit frequency for V2-V10, updated footnote a to align with visit frequency	Correction
1.3. Schedule of Activities	Period II – Q2W visit frequency	Alignment with Q2W visit frequency for V2-V10
	Period III - Clarify that V801 is not needed if more than 12 weeks have passed since last dose of IP at V25 or study discontinuation	Clarification
1.3.2. Period II – Treatment Visits 2-15	Orthostatic BP and pulse are measured at V2, V8, V12, V15, and unscheduled visits, sitting BP, pulse, and temperature will be measured at all visits	Clarification
	MRI notes edited to align with Q2W visit frequency	Alignment with Q2W visit frequency for V2-V10
	Removed footnote a to align with Q2W visit frequency	Alignment with Q2W visit frequency for V2-V10

Section # and Name	Description of Change	Brief Rationale
1.3.3. Period II – Treatment Visits 16-25	Amyloid PET scan note regarding ED visit revised to 3 months from last amyloid PET scan	Correction
4.1.1. Treatment Arms and Titration Regimen Outline	Treatment arms 3 and 4 established; removal of treatment arms 3 option 2 and 4 option 2 and the language around this	Clarification
	Removed "only if donanemab Q2W dosing regimen is chosen; otherwise these visits will be skipped"	Alignment with visit/dosing frequency
4.3. Justification for Dose	Built-in dosing pauses updated to align with current dosing regimens	Clarification
5.2. Exclusion Criteria	Addition of "<5 half-lives prior to randomization" to Exclusion Criterion 22	Clarification
6.3. Assignment to Study Intervention	Clarified stratification regarding PET scan results and APOE genotype	Clarification
8.2.1. Physical/Neurological Examinations	Addition of "neurological" to align with SoA	Correction to align with SoA
8.2.2. Vital Signs	Clarified vital signs, including temperature, will be measured at all visits	Clarification
	Clarified sitting BP is measured at all visits	Clarification
	Clarified orthostatic BP and pulse to be measured supine and standing	Clarification
8.2.5. Suicidal Ideation and Behavior Risk Monitoring	Corrected C-SSRS to be administered at V2 per the SoA	Correction to align with SoA
	Clarified study partner may be present in person or on phone for all days C-SSRS is administered	Clarification
8.4. Pharmacokinetics	Addition of PK sample collection regarding IP discontinuation	Clarification
9.3.1. General Considerations	Alignment with objective tables for 76 weeks (corresponding visit V25) assessment	Editorial

Section # and Name	Description of Change	Brief Rationale
Throughout the protocol	Minor editorial changes	Clarification/editorial

# 1. Protocol Summary

# 1.1. Synopsis

#### **Protocol Title:**

Investigating the Effect of Different Donanemab Dosing Regimens on ARIA-E and Amyloid Lowering in Adults with Early Symptomatic Alzheimer's Disease

#### **Brief Title:**

Exploration of Different Donanemab Dosing Regimens

# **Regulatory Agency Identifier Numbers:**

IND: 109157

EU trial number: 2022-502268-18-00

#### **Rationale:**

This study will investigate different donanemab dosing regimens and their effect on the frequency and severity of ARIA-E in adults with early symptomatic Alzheimer's disease (AD) and explore patient characteristics that might predict risk of ARIA.

# Objectives, Endpoints, and Estimands:

Objectives	Endpoints
Primary	
To assess the effect of alternative donanemab dosing regimens versus the standard donanemab dosing regimen on ARIA-E frequency	Proportion of participants with any occurrence of ARIA-E by Week 24
Secondary	
To assess the effect of alternative donanemab dosing regimens versus standard donanemab dosing regimen on ARIA-E frequency	Proportion of participants with any occurrence of ARIA-E by Week 52
To assess the effect of alternative donanemab dosing regimens versus standard donanemab dosing regimen on brain amyloid deposition	Change from baseline in brain amyloid plaque deposition as measured by amyloid PET scan through  Week 24  Week 52  Week 76

To evaluate the effect of alternative donanemab dosing regimens on ARIA events	
 
Proportion of participants with any occurrence of ARIA-H by
 
Week 24
 
Week 52
 
ARIA-E and ARIA-H by severity
 

To assess peripheral PK and presence of anti-donanemab antibodies	
 
Serum PK of donanemab
 
ADAs against donanemab, including TE-ADAs and neutralizing antibodies
 

Abbreviations: AB = amyloid-beta peptide; ADA = antidrug antibody; ARIA = amyloid-related imaging abnormalities; PK = pharmacokinetic.

#### **Estimand**

The primary clinical question of interest is:

What is the reduction in the frequency of ARIA-E events at Week 24 in participants with early symptomatic AD treated with an alternative donanemab dosing regimen compared to the standard donanemab dosing regimen, regardless of discontinuation or interruption of donanemab dosing for any reason and regardless of change in background AD medication?

## **Overall Design**

This is a multicenter, randomized, double-blind, Phase 3b study in adults with early symptomatic AD. Early symptomatic AD refers to the combination of 2 stages, mild cognitive impairment and mild AD dementia.

The study duration will be up to approximately 91 weeks and includes a

- screening period
- double-blind treatment period, and
- posttreatment follow-up.

The visit frequency is every 2 weeks for Visits 2-10 and every 4 weeks thereafter.

The treatment duration will be up to approximately 72 weeks.

If a participant meets amyloid plaque reduction criteria at Visit 12 (Week 24) or Visit 19 (Week 52), they will no longer receive treatment, and the study-site personnel may conduct Visits 13, 14, 16, 17, 18, 20, 21, 23, and 24 by telephone.

#### **Brief Summary:**

This study is intended to assess

- alternate donanemab dosing regimens that could potentially reduce the risk of ARIA-E frequency, severity, symptoms
- baseline and treatment response characteristics, including magnetic resonance imaging (MRI) and blood-based biomarkers, that might predict risk of ARIA-E, and

• amyloid lowering of alternate dosing regimens.

Magnetic resonance imaging of the brain will be used to check for evidence of ARIA-H or ARIA-E, and other clinically relevant safety findings.

Amyloid positron emission tomography (PET) scans provide a quantitative assessment of amyloid plaque deposition in the brain and can serve as a biomarker of clearance of amyloid deposits.

Part of the study eligibility criteria is determined by amyloid PET scans. Additional amyloid PET scans will be performed during the study.

#### Study partners

Each participant must have a study partner.

A second study partner may serve as backup. The study partners are required to accompany the participant for signing consent. Certain study visits require that a study partner is available by telephone if not accompanying the participant at the visit.

If a study partner must withdraw from study participation, a replacement may be allowed at the investigator's discretion.

#### **Study Population:**

In general, an individual may take part in this study if they

- Are 60 to 85 years of age, at the time of signing the informed consent.
- Have gradual and progressive change in memory function for ≥6 months from time of signing the informed consent.
- Have a Mini Mental State Examination (MMSE) score of 20 to 28 at Visit 1. The MMSE is a brief instrument used to assess cognitive function.
- Have an amyloid PET scan result that shows the presence of amyloid pathology.

In general, an individual may not take part in this study if they

- Have significant neurological disease affecting the central nervous system other than AD, that may affect cognition or ability to complete the study, including but not limited to, other dementias, serious infection of the brain, Parkinson's disease, multiple concussions, or epilepsy or recurrent seizures, except febrile childhood seizures.
- Have a condition that in the investigator's opinion could interfere with the analyses of this study, or a current serious or unstable illness.
- Have a life expectancy of less than 24 months.
- Are not able to complete the MRI imaging procedures due to issues, such as claustrophobia, or have metal implants or a cardiac pacemaker.
- Are not able to complete the PET procedure or have sensitivity to the amyloid PET tracer used in the procedure.
- Have previously received donanemab or treatment before with passive anti-amyloid immunotherapy <5 half-lives prior to randomization.

#### **Number of Participants:**

Approximately 800 participants will be randomly assigned to 1 of 4 treatment arms in a 1:1:1:1 ratio.

#### **Intervention Groups and Duration:**

There will be 4 treatment arms in this study.

All participants will receive a dosing regimen that includes donanemab, but at different dose levels and frequency of dosing. Placebo is given at specific visits to preserve the blind for the different dosing regimens. All dosing is administered by intravenous infusion.

After Week 16, all participants are targeted to receive the maximum donanemab dose of 1400 mg monthly until they meet the dose stopping criteria or until the end of the study.

#### **Ethical Considerations of Benefit/Risk:**

[figure not shown]
A potential key benefit for participation in this study is the delay in cognitive and functional decline associated with AD.

The potential risks associated with participation in this study are the occurrence of ARIA and infusion-related reactions. These risks are observed with beta amyloid plaque-targeted therapies, including donanemab.

Given the seriousness and limited treatments for AD, donanemab provides a clinically meaningful treatment alternative. Considering the measures taken to minimize risk to participants, the potential benefit-risk balance for this study is acceptable for testing different dosing regimens that may reduce the risk of ARIA.

**Data Monitoring Committee: Yes** 

# 1.2. Schema

<sup>a The visit frequency is every 2 weeks for Visits 2-10, and every 4 weeks thereafter.

Note: If a participant meets amyloid plaque reduction criteria defined by the Sponsor, as measured by amyloid PET scan, at Visit 12 (Week 24) or Visit 19 (Week 52), the participant will discontinue study intervention and stay in the study for the remaining study visits.

# 1.3. Schedule of Activities (SoA)

Three tables describe the SoA.

Table 1 (Section 1.3.1) describes Period I Screening.

Table 2 (Section 1.3.2) describes Period II Treatment Visits 2-15.

Table 3 (Section 1.3.3) describes Period II Treatment Visits 16-25, the Early Discontinuation Visit, and Period III Posttreatment Follow-Up Visit 801.

# Period I - Screening

Visit 1 procedures may be conducted over more than 1 day if all activities are completed within the allowable visit tolerance.

Screening should not extend past 49 days. Sponsor may strictly control toward end of study enrollment. If the PET or MRI results are delayed due to technical or logistical circumstances, it is not considered a protocol deviation.

#### Period II - Treatment

The visit frequency is every 2 weeks for Visits 2-10, and every 4 weeks thereafter. See Section 4.1.1 for more treatment arm information.

#### **Early discontinuation**

If a participant discontinues the study before Visit 25, perform ED assessments. After the ED Visit, the participant proceeds to Period III to complete the follow-up visit, if possible.

# Period III - Follow-up

Visit 801 occurs at least 12 weeks after the last dose of IP. V801 is not needed if more than 12 weeks have passed since last dose of IP at V25 or study discontinuation.

#### **Telephone visits**

If a participant meets amyloid plaque reduction criteria at Visit 12 or Visit 19 and discontinues study intervention, the study-site personnel may conduct Visits 13, 14, 16-18, 20, 21, 23, and 24 by telephone. See Sections 4.1.1 and 7.1 for details.

# 1.3.1. Period I - Screening

I5T-MC-AACQ	Period I Screening	Notes
Visit Number	Visit 1	
Day Relative to Randomization	-49 to -1	
Tolerance Interval for Visit (Days)	≤49 before Visit	
Entry and administrative procedures		
Informed Consent - Participant	X	The participant informed consent form must be signed before any protocol-specific tests or procedures are performed.
Informed Consent - Study Partner	X	The study partner informed consent form must be signed before any protocol-specific tests or procedures are performed.
Inclusion/exclusion review	X	Review inclusion and exclusion criteria as information becomes available.
Demographics	X	Includes year of birth, sex, ethnicity (where permissible), and race.
Preexisting conditions and medical history	X	Collect all ongoing conditions and medical history.
Substance use (alcohol, caffeine, tobacco use, and nicotine replacement)	X	
Concomitant medications	X	
Adverse events (AEs)	X	Any events that occur after signing the informed consent are considered AEs as defined in Section 10.3.
Safety assessments		
Height	X	
Weight	X	
Vital signs	X	Measure vital signs after the participant has been sitting at least 5 min, and before obtaining a local ECG tracing, or collection of blood samples for laboratory testing.  Collect temperature with sitting vitals.
Physical/neurological examination	X	See the Manual of Operations for details.

I5T-MC-AACQ	Period I	Notes
	Screening	
Visit Number	Visit 1	
Day Relative to Randomization	-49 to -1	
Tolerance Interval for Visit (Days)	≤49 before Visit 2	
ECG 12-lead (single, local)	X	Collect ECG before blood sample collection. Unscheduled ECGs may be performed at the discretion of investigator.
Patient-reported outcomes (paper)		
MMSE	X	Participants must meet MMSE criteria before any other screening procedures are performed. See Section 5.5 for rescreening criteria.  Administer the MMSE prior to medical procedures that could be stressful to the participant, for example before a blood draw.
Laboratory tests and sample collections		Blood draws for screening should be collected at the same time.
Hematology	X	
Clinical Chemistry	X	
Urinalysis	X	
Apolipoprotein E (ApoE)	X	Results will not be provided to the investigators.
Plasma pTau	X	Results will not be provided to the investigators.
Stored samples		Collect only where available and allowed per local regulations.
Genetics Sample	X	
Exploratory Biomarker Samples	X	

I5T-MC-AACQ	Period I Screening	Notes
Visit Number	Visit 1	
Day Relative to Randomization	-49 to -1	
Tolerance Interval for Visit (Days)	≤49 before Visit 2	
Screening PET scans and MRI		
Amyloid PET	X	The participant should meet all other eligibility criteria before the amyloid PET scan and MRI. If
MRI of brain	X	imaging results are received after the screening window, the participant remains eligible contingent on meeting the other eligibility criteria. If the investigator feels it is necessary, they may repeat the screening labs.  A historical amyloid PET scan may be submitted for eligibility if performed within 12 months of Visit 2, randomization. The acceptance of a historical scan is at the discretion of the Sponsor. See Section 8.2.7 for MRI details.
Randomization and dosing		
Register visit with IWRS	X	

# 1.3.2. Period II - Treatment Visits 2-15

I5T-MC-AACQ		Period II Treatment												Notes				
Visit Number	2	3	4	5	6	7	8	9	10	11	12	13	14	15				
Week Relative to Randomization	0	2	4	6	8	10	12	14	16	20	24	28	32	36				
Tolerance Interval for Visit (Days)	0	±7	±7	±7	±7	±7	±7	±7	±7	±7	±7	±7	±7	±7				
Administrative																		
Inclusion/exclusion review															Confirm participant meets all Visit 1 eligibility criteria before proceeding to Visit 2 procedures.			
Concomitant medications	X	X	X	X	X	X	X	X	X	X	X	X	X	X	·			
Adverse events (AEs)	X	X	X	X	X	X	X	X	X	X	X	X	X	X	Any event(s) that occur after signing the informed consent are considered AEs as defined in Section 10.3.			
Safety Assessments																		
Weight	X						X				X			X				
Vital signs and temperature	X	X	х	X	X	х	х	Х	X	X	X	X	X	X	Sitting BP, pulse, and temperature will be measured at all visits. In addition, orthostatic BP and pulse will be measured at V2, V8, V12, V15, and unscheduled visits.  See Section 8.2.2. Note: Measure BP and pulse for suspected hypersensitivity events when able to do so. Do not collect if visit is conducted by telephone.			

I5T-MC-AACQ		Period II Treatment													Notes		
Visit Number	2	3	4	5	6	7	8	9	10	11	12	13	14	15			
Week Relative to Randomization	0	2	4	6	8	10	12	14	16	20	24	28	32	36			
Tolerance Interval for Visit (Days)	0	±7	±7	±7	±7	±7	±7	±7	±7	±7	±7	±7	±7	±7			
Administrative																	
Physical/neurological examination	X						X				X			X	See the Manual of Operations for details. Note any clinically significant changes from baseline on the AE CRF.		
Clinician-administered Assessments (Paper)																	
C-SSRS screening/baseline	X														AE collection should occur prior to the collection of the C-SSRS.		
C-SSRS since last assessed			X		X		X		X	X	X	X	X	X			
Laboratory tests and sample collections															Collect samples before dosing, unless indicated below. See Section 10.2 for details of testing included in panels.		
Hematology	X						X				X			X			
Clinical Chemistry	X						X				X			X			
High-sensitivity C-Reactive Protein	X		X		X		X				X			X			
Neurofilament Light chain	X		X		X		X				X			X			
Glial fibrillary acidic protein	X		X		X		X				X			X			
sTREM2	X		X		X		X				X			X	Collect only where available and allowed per local regulations.		
Amyloid-Beta 40 and 42	X		X		X		X				X			X			
Plasma pTau	X		X		X		X				X			X			
Pharmacokinetic Samples (Predose)			X		X		X				X				Sample may be collected from the IV site prior to the infusion.		

I5T-MC-AACQ		Period II Treatment													Notes
Visit Number	2	3	4	5	6	7	8	9	10	11	12	13	14	15	
Week Relative to Randomization	0	2	4	6	8	10	12	14	16	20	24	28	32	36	
Tolerance Interval for Visit (Days)	0	±7	±7	±7	±7	±7	±7	±7	±7	±7	±7	±7	±7	±7	
Administrative															
Pharmacokinetic Samples (Postdose)	X		X				X				X				Collect within 30 min after the end of infusion. Collect from different arm than one used for the infusion.
Immunogenicity Samples	X		X		X		X				X				Collect before the infusion when applicable and possible.
Stored Samples															
Exploratory Biomarker Samples	X		X		X		X				X			X	Collect before the infusion where allowed per local regulations.
Other Safety Measures															
MRI of brain	X				X				X				Visit 4: Perform and review MRI before the Visit 4 dose and at least 21 days after the first infusion. Visit 8: Perform and review MRI before the Visit 8 dose. If dosing was missed in visits before Visit 8: perform and review an additional MRI before seventh dose. See Section 8.2.7.1 for MRI sequence details for each visit. Unscheduled MRIs may be performed at the discretion of investigator.		
Additional Efficacy Measures															
Amyloid PET scan											X				

I5T-MC-AACQ						]	Notes								
Visit Number	2	3	4	5	6	7	8	9	10	11	12	13	14	15	
Week Relative to Randomization	0	2	4	6	8	10	12	14	16	20	24	28	32	36	
Tolerance Interval for Visit (Days)	0	±7	±7	±7	±7	±7	±7	±7	±7	±7	±7	±7	±7	±7	
Administrative															
Randomization and Dosing															
Randomization using IWRS	X														
Register visit with IWRS	X	X	X	X	X	X	X	X	X	X	X	X	X	X	
Dispense study intervention using IWRS	X	X	X	X	X	X	X	X	X	X	X	X	X	X	
Administer study intervention	X	X	X	X	X	X	X	X	X	Х	X	X	X	X	The participant must be observed for a minimum of 30 min following the end of each infusion.  Visits 2 to 10: Dosing intervals must be more than 7 days apart.  Visits 10 to 15: Dosing intervals must be greater than or equal to 21 days apart.

# 1.3.3. Period II - Treatment Visits 16-25, the Early Discontinuation Visit, and Period III Posttreatment Follow-Up Visit 801

I5T-MC-AACQ		Period II Treatment											Notes
Visit Number	16	17	18	19	20	21	22	23	24	25	ED	801	
Week Relative to Randomization	40	44	48	52	56	60	64	68	72	76		84	
Tolerance Interval for Visit (Days)	±7	±7	±7	±7	±7	±7	±7	±7	±7	±7		±14	
Administrative													
Concomitant medications	X	X	X	X	X	X	X	X	X	X	X	X	
Adverse events (AEs)	X	X	X	X	X	X	X	X	X	X	X	X	Any events that occur after signing the informed consent are considered AEs as defined in Section 10.3.
Safety Assessments													
Weight				X			X			X	X		
Vital signs and temperature	X	X	X	X	X	X	X	X	X	X	X	X	See Section 8.2.2. For unscheduled visits, measure orthostatic BP and pulse. Do not collect if visit is conducted by telephone.
Physical/neurological examination				X			X			X	X		See the Manual of Operations for details.  Note any clinically significant changes from baseline on the AE CRF.
Clinician-Administered Assessments (Paper)													
C-SSRS since last assessed	X	X	X	X	X	X	X	X	X	X	X	X	AE collection should occur prior to the collection of the C-SSRS.
Laboratory Tests and Sample Collections													Collect samples before dosing, unless indicated below. See Section 10.2 for details of testing included in panels.
Hematology				X			X			X	X		

I5T-MC-AACQ		Period II Treatment										Period III	Notes		
Visit Number	16	17	18	19	20	21	22	23	24	25	ED	801			
Week Relative to Randomization	40	44	48	52	56	60	64	68	72	76		84			
Tolerance Interval for Visit (Days)	±7	±7	±7	±7	±7	±7	±7	±7	±7	±7		±14			
Clinical Chemistry				X			X			X	X				
High-sensitivity C-Reactive Protein				X			X			X	X				
Neurofilament light chain				X			X			X	X				
Glial fibrillary acidic protein				X			X			X	X		Collect only where available and allowed		
sTREM2				X			X			X	X		per local regulations.		
Amyloid-Beta 40 and 42				X			X			X	X				
Plasma pTau				X			X			X	X				
Pharmacokinetic Samples (Predose)				X									May be collected from the IV site before the infusion.		
Pharmacokinetic Samples (Postdose)				X									Collect within 30 min of infusion completion. Collect from different arm than one used for the infusion.		
Pharmacokinetic Samples (Random)										X	X	X	Do not collect if the last infusion was >6 months prior to the scheduled visit.		
Immunogenicity Samples				X						X	X	X	Collect before infusion when applicable and possible.		
Stored Samples															
Exploratory Biomarker Samples				X			X			X	X		Collect before infusion unless not allowed or possible due to local regulation.		

I5T-MC-AACQ		Period II Treatment											Notes
Visit Number	16	17	18	19	20	21	22	23	24	25	ED	801	
Week Relative to Randomization	40	44	48	52	56	60	64	68	72	76		84	
Tolerance Interval for Visit (Days)	±7	±7	±7	±7	±7	±7	±7	±7	±7	±7		±14	
Other Safety Measures													
MRI of the brain				X							X		See Section 8.2.7.1 for MRI sequence details for each visit. Unscheduled MRIs may be performed at the discretion of investigator. ED Visit: Conduct only if ED occurs more than 6 wk from the previous MRI.
Additional Efficacy Measures													
Amyloid PET scan				X						X	X		ED Visit: Conduct only if ED occurs after 3 or more months from the last amyloid PET scan.
Randomization and Dosing													
Register visit with IWRS	X	X	X	X	X	X	X	X	X	X	X	X	
Dispense study intervention using IWRS	X	X	X	X	X	X	X	X	X				
Administer study intervention	X	X	X	X	X	X	X	X	X				The participant must be observed for a minimum of 30 min following the end of each infusion.  Dosing intervals must be more than 21 days apart.

Abbreviations: AE CRF = AE case report form; BP = blood pressure; C-SSRS = Columbia-Suicide Severity Rating Scale; ED = early discontinuation; IWRS = interactive web-response system; IV = intravenous; MMSE = Mini Mental State Examination; MRI = magnetic resonance imaging; PET = positron emission tomography; Q2W = every 2 weeks; sTREM2 = soluble triggering receptor expressed on myeloid cells 2.

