## 4.3. Justification for Dose

The standard donanemab dosing regimen has a titration schedule of 700 mg IV Q4W for the first 3 doses and then 1400 mg IV Q4W. This study will investigate alternative dosing regimens that may potentially reduce the frequency and/or severity of ARIA-E.

The doses and frequency were selected based on human safety, efficacy, PK, and PD data from Phase 1-3 studies.

The goal is to investigate at least 3 additional dose regimens in addition to the standard donanemab regimen. The dosing regimen options are detailed in Section 4.1.1. These dosing regimens include either built-in dosing pause of 8 weeks between infusions, or administering a lower dose more frequently (Q2W), resulting in a lower maximum concentration but with the same monthly exposure compared to the standard donanemab regimen. All of the dosing regimens are anticipated to result in robust plaque clearance.

It is hypothesized that 8-week dosing interval will allow time for potential asymptomatic ARIA to resolve and may decrease the risk of ARIA exacerbation (Salloway et al. 2022).

Administering a lower dose, compared with the standard donanemab regimen, will result in a lower maximum concentration ( $C_{max}$ ). It is hypothesized that a lower  $C_{max}$  and a slower increase in serum concentration may reduce ARIA risk (Hayato et al. 2020; Salloway et al. 2022).

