# **6.5.** Study Intervention Compliance

Study intervention will be administered under medical supervision by the investigator or designee. The dose of study intervention and study participant identification will be confirmed prior to the time of dosing. The date and time of each dose administered will be recorded in the source documents and in the CRF.

Any infusion at which 75% or more of the infusion solution is given will be considered a complete infusion. If a participant attends a visit but does not receive a complete infusion, for example, due to technical complications, every effort should be made to complete the infusion within 24 hours of preparation, except if an infusion reaction occurs that prevents rechallenge. If less than 75% of the infusion solution is given, this must be recorded as an incomplete infusion on the CRF.

Missed infusions should be recorded on the CRF. If at any time it is discovered that the participant has not completed proper dosing during the titration phase, the Sponsor should be contacted prior to the subsequent infusions to discuss the possibility of completing a proper titration phase, if needed.

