# 8.3.3.1. Amyloid-Related Imaging Abnormalities (ARIA)

While most cases of ARIA are asymptomatic, serious and life-threatening cases have been reported. Available data suggest serious cases are most likely to occur early in dosing, after the first, second, or third infusion of standard donanemab dosing.

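### Visits 2-10 have no explicit minimum between donanemab doses planned 4 weeks apart, so one interval between Visits 4 and 10 can be 16 days, although about 21 days is required from Visit 10

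*Protocol*

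**What the plan says.** The schedule in Protocol Section 1.3.2 counts visits by "Week Relative to Randomization". Visit 2 has no tolerance and Visits 3-15 have ±7 days each. The study-drug row gives two spacing rules: "Visits 2 to 10: Dosing intervals must be more than 7 days apart" and "Visits 10 to 15: Dosing intervals must be greater than or equal to 21 days apart". For Visits 16-25, Section 1.3.3 says "Dosing intervals must be more than 21 days apart".

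Section 4.1.1 shows what is infused. Arms 1 and 3 receive donanemab at Visits 2, 4, 6, 8 and 10, with placebo at Visits 3, 5, 7 and 9. Arm 2 receives donanemab at Visits 2, 6, 8 and 10. Arm 4 receives donanemab at every visit from 2 to 10. Section 4.3 describes the standard regimen as "700 mg IV Q4W for the first 3 doses and then 1400 mg IV Q4W".

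On imaging, the Section 1.3.2 notes place the Visit 4 MRI at least 21 days after the first infusion and before that visit's dose. For the next scan they say "Visit 8: Perform and review MRI before the Visit 8 dose", with no minimum number of days since the previous dose.

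**The concern.** The more-than-7-day rule acts on consecutive infusions. In Arms 1-3 the placebo infusions between monthly doses satisfy it without protecting the interval between active doses. The stretch without a floor, Visits 4-10, contains the dose steps: 700 to 1400 mg at Visits 6-8 in Arm 1, and 700 to 1050 to 1400 mg at Visits 4-8 in Arm 3.

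Section 8.3.3.1 reports that "serious cases are most likely to occur early in dosing, after the first, second, or third infusion of standard donanemab dosing". In Arm 1 the intervals after the second and third infusions are Visits 4-6 and 6-8. Section 4.3 also hypothesises that a slower rise in serum concentration may reduce ARIA risk, and closely spaced doses work against that. The MRI before the Visit 8 dose partly covers Visits 6-8. No scheduled MRI falls between the Visit 4 and Visit 6 doses or between the Visit 8 and Visit 10 doses.

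At stake are participant safety during escalation and fidelity to the regimens being compared.

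**Working it through.** The protocol states no minimum active-dose interval for this period, so there is no figure to reproduce. The check derives one.

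**Inputs (Sections 1.3.2 and 4.1.1).** Visit day windows are:

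| Visit | Permitted days |
|---|---|
| 2 | 0 |
| 4 | 21-35 |
| 5 | 35-49 |
| 6 | 49-63 |
| 8 | 77-91 |
| 10 | 105-119 |
| 11 | 133-147 |

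More than 7 days means at least 8 whole days between consecutive infusions.

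**Shortest active-dose intervals**

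- Visit 2 to Visit 4: 21 − 0 = 21 days, set by the window.
- Visit 2 to Visit 6 (Arm 2): 49 − 0 = 49 days.
- Visits 4-6, 6-8 and 8-10 with the middle placebo given: 8 + 8 = 16 days. Example: days 35, 43 and 51, all inside their windows.
- The same intervals with the placebo missed: the windows alone give 49 − 35 = 14, 77 − 63 = 14 and 105 − 91 = 14 days.
- Visit 10 to Visit 11: the windows alone would give 133 − 119 = 14 days. Here the protocol adds its 21-day floor.

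The 16-day minimum therefore applies to three intervals in Arms 1 and 3 and to two (Visits 6-8 and 8-10) in Arm 2.

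**Do short intervals accumulate?** No.

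- Visit 4 to Visit 8 takes at least 77 − 35 = 42 days, and Visit 6 to Visit 10 at least 105 − 63 = 42 days. Two adjacent intervals under 21 days would total at most 20 + 20 = 40 days, so they cannot both occur.
- If Visits 4-6 take 16 days, Visit 6 is at latest day 35 + 16 = 51, and the next interval is at least 77 − 51 = 26 days.
- Visit 4 to Visit 10 takes at least 105 − 35 = 70 days, against 84 planned.

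**How often?** The documents do not say, so visit-day scatter is assumed. For each setting, 2,000,000 schedules were simulated with independent deviations from nominal (rounded normal, or uniform from −7 to +7). Only schedules inside all windows and with consecutive gaps of at least 8 days were kept.

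| Scatter | Any interval <21 days, Arms 1 and 3 | Arm 2 | Any 16-day interval (Visits 4-10) |
|---|---|---|---|
| SD 2 days | 0.8% | 0.5% | about 0.001% |
| SD 3 days | 5.3% | 3.5% | 0.05% |
| SD 4 days | 9.6% | 6.3% | 0.16% |
| Uniform | 17% | 11% | 0.6% |

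With about 200 participants per arm, the normal settings correspond to roughly 2, 11 and 19 participants in each of Arms 1 and 3 (200 × 0.008, 0.053 and 0.096).

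**The case against.** The strongest reply is that 16 days is an extreme case and the frequencies are pessimistic. They treat visit deviations as independent, whereas a late visit often pushes the next one late too, which keeps intervals closer to plan. With a correlation of 0.5 between adjacent visits, the share with any interval under 21 days in Arms 1 and 3 falls to 0.3%, 3.3% and 7.1% at SD 2, 3 and 4. At 0.7 it is 0.03%, 1.3% and 4.0%. The uniform setting discards about 79% of simulated schedules for breaking the 8-day rule, so it is a poor model of site behaviour. All of this stands.

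The safety link is also inferred. Section 8.3.3.1 ties serious ARIA to infusion number, not spacing. Nothing in the documents says that 16-20 days is riskier than 21, or why the later floor was set. The missing MRI between Visits 4 and 6 would be missing at 28 days too. That also stands, and it keeps the point minor.

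Other safeguards exist. Investigators may hold a dose increase or pause dosing for ARIA (Sections 6.6 and 7.1.2), and more than one suggestive symptom triggers an unscheduled MRI (Section 8.3.3.1). If dosing was missed before Visit 8, an extra MRI precedes the seventh dose. For incomplete titration, Section 6.5 says "the Sponsor should be contacted prior to the subsequent infusions to discuss the possibility of completing a proper titration phase". But the last two respond to missed or improper dosing. A 16-day interval with every infusion given is compliant and triggers neither.

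Finally, a 21-day rule cannot apply to every infusion when all arms are infused every 2 weeks for blinding. That is correct, but it does not prevent a rule for alternate visits.

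**Conclusion.** The point holds as a minor one. The protocol has no explicit floor between active doses planned 4 weeks apart from Visit 4 to Visit 10. Its rules allow a 16-day interval there, or 14 days if the intervening placebo is missed, while about 21 days is required from Visit 10. The minima follow directly from the stated windows and rules. The frequencies rest on assumed visit scatter and are probably upper-side figures if delays carry forward.

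The windows are the same in every blinded arm and short intervals cannot be adjacent, so no bias in the Week 24 ARIA-E comparison is shown. The Manual of Operations and Pharmacy Preparation Instructions were not available. Neither the protocol nor the SAP mentions a spacing rule in them. If one exists, a cross-reference would close the point.

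Separately, Section 1.3.2 words the later floor as at least 21 days and Section 1.3.3 as more than 21 days, a one-day editorial mismatch.

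**What to change.** In Section 1.3.2, keep the more-than-7-day rule for consecutive infusions and add one blinded rule for all arms, checked in the IWRS: infusions at Visits 2, 4, 6, 8 and 10 must be at least 21 days apart. In Section 1.3.3, change the wording to at least 21 days to match.

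The rule fits from every permitted starting day. At the latest, Visit 4 on day 35 puts Visit 6 at day 56 or later (window 49-63). Visit 6 on day 63 puts Visit 8 at day 84 or later (77-91). Visit 8 on day 91 puts Visit 10 at day 112 or later (105-119). Arm 4's two-weekly dosing is kept, and the identical rule in all arms preserves the blind.

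The cost is one added line, one small wording change, an IWRS check, and the ethics approval that Section 10.1.1 requires for amendments. Sites lose some flexibility: after a late even-numbered visit, the next even-numbered visit cannot be early.
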